16.3 Statistical Design

This is a screening protocol and is not designed to test a specific hypothesis. All analyses will be done in descriptive fashion only.

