16.4 Sample Size

The total sample size of COLOMATE will be approximately 500 patients. The sample size for each individual companion trial will depend on the prevalence of the actionable genomic alterations and availability of companion trials.

For ACCRU-GI-1611, there is no formal hypothesis testing.

Given 500 patients, assume X% of patients can be assigned to a companion trial, the corresponding 95% confidence interval is shown in the table below. The sample size of 500 allows us to have good precision (i.e. confidence interval width less than 10%) in estimating the proportion of patients recommended into a companion trial.

Assumed proportion of patients can be recommended to a companion trial $(X\%)$	Confidence interval
10%	(7.37%, 12.63%)
20%	(14.49%, 23.51%)

30%	(25.98%, 34.02%)
40%	(35.71%, 44.29%)
50%	(45.62%, 54.38%)
60%	(55.71%, 64.29%)

Assume 40% of the patients will be recommended to a companion trial (i.e. N=200) and further assume X% of patients would enrolled into the recommended trial, the corresponding 95% confidence interval is shown in the table below. With a sample size of 500 and 40% of patients recommended, we also have decent precision (i.e. confidence interval width less than 15%) in estimating the proportion of patients enrolled into the recommended trials among those recommended. Given the fact that ACCRU-GI-1611 is actively opening additional companion trials, we do not expect less than 40% of patients will be recommended to a companion trial.

Proportion of patients enrolled into the recommended companion trial (X%)	Confidence interval
5%	(1.98%, 8.02%)
10%	(5.84%, 14.16%)
15%	(10.05%, 19.95%)
20%	(14.46%, 25.54%)
25%	(19.00%, 31.00%)
30%	(23.65%, 36.35%)

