16.5 Analysis Plan

16.51 Primary Endpoints

For the analysis of the first primary endpoint, the proportion of patients who
have an actionable genomic profile will be calculated. This is defined as the
total number of eligible patients who have an actionable genomic profile
divided by the total number of eligible patients whose genomic profile is
available for COLOMATE steering committee review.

A patient may come back to ACCRU-GI-1611 for subsequent screening (see sections 7.5, 7.5, and 7.6); therefore, a patient can contribute information to the first primary endpoint more than once.

- Our goal is to have at least 20% of patients have actionable genomic profile. The endpoint will be presented as a point estimate along with a 95% confidence interval (by Wald asymptotic confidence limit).
- For the analysis of the second primary endpoint, the proportion of patients that enroll in the companion trial recommended by the COLOMATE committee will be calculated. This is defined as the total number of eligible patients that enroll in the recommended companion trial divided by the total number of eligible patients who have an actionable genomic profile.

A patient may come back to ACCRU-GI-1611 for subsequent screening (see sections 7.4, 7.5, and 7.6); therefore a patient can contribute information to

the second primary endpoint more than once.

• Our goal is to enroll at least 75% of patients who have an actionable genomic profile. The endpoint will be presented as a point estimate along with a 95% confidence interval (by Wald asymptotic confidence limit).

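### For companion trial enrolment at low rates (about 5–10%, N=200), the prespecified Wald interval covers less than its nominal 95% and its upper limit is too low; Wilson limits are a cheap, minor improvement

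*Combined protocol and SAP*

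**What the plan says.** Section 16.51 uses the same reporting rule for each primary endpoint: "The endpoint will be presented as a point estimate along with a 95% confidence interval", the interval being obtained "by Wald asymptotic confidence limit". No other interval is named.

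Section 16.4 sets the planning figures. For the first endpoint (actionable genomic profile): "The total sample size of COLOMATE will be approximately 500 patients", with intervals tabulated for 10% to 60%. For the second (companion trial enrolment): "Assume 40% of the patients will be recommended to a companion trial (i.e. N=200"), with intervals tabulated for 5% to 30%. The precision aim there is "confidence interval width less than 15" percentage points; for the first endpoint it is less than 10.

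The goals in Section 16.51 are "Our goal is to have at least 20% of patients have actionable genomic profile" and "Our goal is to enroll at least 75% of patients who have an actionable genomic profile". The second goal lies well outside the enrolment table, which stops at 30%. Section 16.3 adds: "All analyses will be done in descriptive fashion only".

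**The concern.** With no hypothesis test, the two 95% intervals are the trial's only formal statement of uncertainty, and Section 16.4 justifies the sample size entirely by their width. The Wald interval is symmetric about the estimate and takes its standard error from that same estimate. When the count is small, a low estimate therefore gets both a low centre and a short interval. The expected result is coverage below 95%, with most misses on one side.

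The lowest tabulated enrolment rates are where this should show: 5% of 200 is 10 patients. If enrolment turns out that low, the reported upper limit would understate how high the true rate could plausibly be.

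**Working it through.** **Inputs.** n=500 and N=200, the tabulated rates and the 75% goal (Sections 16.4 and 16.51); two-sided 95%, z = 1.96. Records are treated as independent.

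**Step 1: reproduce the plan's tables.** Wald limits are p ± 1.96·√[p(1−p)/n]. At p=0.05, N=200: √(0.05×0.95/200) = 0.01541, times 1.96 = 0.0302, giving (1.98%, 8.02%) as printed. All six N=200 rows reproduce. Five of the six n=500 rows do too. The 20% row prints a lower limit of 14.49%, where the formula gives 16.49%; this looks like a typing error.

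**Step 2: exact coverage by hand at p=0.05, N=200.** Find the counts x whose interval contains 5%, then sum Binomial(200, 0.05) over them.
- Wald: x=5 has upper limit 2.5% + 2.16% = 4.66%, which misses; x=6 has upper limit 5.36%, which covers. At the other end x=17 has lower limit 4.63%, which covers; x=18 has 5.03%, which misses. So 5% is covered for x = 6 to 17. P(X≤5) = 6.23% and P(X≥18) = 1.21%, so coverage is 100 − 6.23 − 1.21 = 92.56%.
- Wilson: 5% is covered for x = 4 to 16. P(X≤3) = 0.90% and P(X≥17) = 2.38%, so coverage is 96.72%.

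**Step 3: the same sum at the other rates, N=200.** Exact coverage jumps with p because counts are whole numbers, so an average over p ± 1 point is shown as well.

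| True rate | Wald, exact | Wald, averaged | Wilson, exact | Wilson, averaged |
|---|---|---|---|---|
| 5% | 92.6% | 92.8% | 96.7% | 95.2% |
| 10% | 92.7% | 94.0% | 95.6% | 95.1% |
| 15% | 94.4% | 94.4% | 94.1% | 95.1% |
| 20% | 94.1% | 94.6% | 95.9% | 95.0% |
| 25% | 93.7% | 94.6% | 95.9% | 95.0% |
| 30% | 94.4% | 94.7% | 94.7% | 95.0% |
| 75% | 93.7% | 94.6% | 95.9% | 95.0% |

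Near 75%, the averaged Wald misses are 3.4% (interval wholly above the truth) and 2.0% (wholly below), against 2.5% nominal each.

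**Step 4: first endpoint, n=500.** Wald covers 94.3% at 10%, 94.9% at 20% and 94.6–95.0% at 30–60%. At exactly 40%, 50% and 60%, Wald and Wilson coverage are identical.

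**Step 5: Wilson limits and widths.** Limits are {p + z²/(2n) ± z·√[p(1−p)/n + z²/(4n²)]} / (1 + z²/n). At p=0.05, N=200: centre (0.05 + 0.00960)/1.01921 = 0.0585; half-width (1.96/1.01921)·√(0.0002375 + 0.0000240) = 0.0311; limits (2.74%, 8.96%). Width is 6.22 points, against 6.04 for Wald. The largest possible Wilson width, at 50%, is 8.73 points at n=500 and 13.73 at N=200, so both width claims survive.

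**The case against.** The strongest objection is that little depends on this. Wald is standard, clearly prespecified and consistent with the planning tables, and the analysis is descriptive. That stands, and it limits the point to a minor one.

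Three stronger readings are tempting, and the documents do not support them.
- **The interval flatters attainment of the 75% goal.** Part of the 93.7% coverage at exactly 75% is a whole-number effect; the average is 94.6%. At an observed 75%, the limits move about half a point, from (69.0%, 81.0%) to (68.6%, 80.5%). Section 16.51 states the goal as a bare proportion and compares no confidence limit with it.
- **Both endpoints are affected.** The first is close to nominal at n=500, so changing it there is for consistency.
- **Coverage could fall below 88%.** If only 20% of 500 were recommended (N=100), Wald would cover 87.8% at a true 5% (91.1% averaged over 4–6%). But 20% is the minimum goal, and Section 16.4 says that fewer than 40% is not expected. This is a sensitivity case only.

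It is also fair to say that Wilson is not a complete correction. At exactly 15%, N=200, it covers 94.1% against 94.4% for Wald. Near 5% it leaves a milder, reversed imbalance: averaged misses are 3.2% above the truth and 1.6% below.

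Finally, Section 16.51 lets a patient count more than once in either endpoint. Wilson assumes independent records just as Wald does. The documents give no repeat rate or within-patient correlation. Under assumed design effects of 1.1, 1.2 and 1.5, nominal 95% coverage would fall to about 93.8%, 92.6% and 89.0% (normal approximation), so that separate issue could be as large as this one or larger.

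**Conclusion.** The concern holds for the second primary endpoint at low enrolment rates. At N=200 the shortfall in coverage is about 2.4 points at 5% (2.2 averaged over ±1 point) and 2.3 points at 10% (1.0 averaged), with upper limits that are too low. At 15–30% and near 75% the average shortfall is about 0.3–0.6 point, too small to matter in practice. The first endpoint needs no correction on coverage grounds.

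These figures assume N=200 and independent records. How much they matter depends on the enrolment rate actually seen, which the documents do not predict beyond the tabulated 5–30% and the 75% goal. This is a minor, inexpensive improvement, not a design flaw.

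**What to change.** In Section 16.51, name the Wilson score interval (without continuity correction) in place of the Wald limit for the second endpoint, and for the first for consistency. Recompute both tables in Section 16.4:

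| n=500 | Wilson 95% | N=200 | Wilson 95% |
|---|---|---|---|
| 10% | (7.67%, 12.94%) | 5% | (2.74%, 8.96%) |
| 20% | (16.73%, 23.73%) | 10% | (6.57%, 14.94%) |
| 30% | (26.15%, 34.16%) | 15% | (10.71%, 20.61%) |
| 40% | (35.80%, 44.35%) | 20% | (15.05%, 26.09%) |
| 50% | (45.63%, 54.37%) | 25% | (19.51%, 31.43%) |
| 60% | (55.65%, 64.20%) | 30% | (24.07%, 36.68%) |

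Reissuing the first table also removes the misprinted 20% row.

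The cost is one phrase, which occurs twice, and two tables. No patients or data are added. The interval is 0.18 point wider at 5% (6.22 − 6.04) and 0.05 point wider at 10% (8.37 − 8.32). Repeat registrations need their own provision, such as one record per patient or a cluster-robust interval; this change does not supply it.

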17.0 Pathology Considerations/Tissue Biospecimens

As specific future analyses are identified, this protocol may be amended and IRB approval obtained.

18.0 Records and Data Collection Procedures

18.1 Submission Timetable

Initial Material(s)

initial Waterial(s)	
CRF	Active-Monitoring Phase (Compliance with Test Schedule Section 4)
Institutional Contacts	30 days (±3 days) after registration
On-Study	
Supporting Documentation: Baseline ¹	
Specimen Submission: Blood - Baseline	
(see Section 14) ²	
Patient Status: Baseline	

- 1. Pathology report confirming adenocarcinoma, all available tumor molecular testing reports (KRAS, NRAS, BRAF, MSI-H, etc.), Guardant360 test results, and COLOMATE Companion Trial Recommendation Form.
- 2. Submit if Guardant360 (cfDNA) test is done after registration to COLOMATE.

Test Schedule Material(s)

1 est Schedule Material(s)		
	Active-Monitoring Phase (Compliance with Test Schedule Section 4)	
CRF		
	At Receipt of	At any
	Guardant360 Testing	occurrence
Consent Withdrawal ¹		X
Consent Withdrawal: Specimen Only ¹		X

CRF	Active-Monitor (Compliance with Test S	
	At Receipt of	At any
	Guardant360 Testing	occurrence
Deviation Form ¹		X
DNA Testing Dates (Internal Use Only-		X
ACCRU Office)		

^{1.} Submit only if applicable.

19.0 Budget

- 19.1 Each site should review the test schedule (Section 4), taking into account local and regional coverage policies, to determine which items are standard of care and which are research at their site. Refer to the payment synopsis for funding provided per accrual for covering study costs, as well as any additional invoiceables that may be allowed.
- 19.2 Tests to be research funded:
 - Guardant360 cfDNA testing at baseline
- 19.3 Other budget concerns: Refer to the payment synopsis for funding provided for covering any costs, as well as any additional invoiceables that may be allowed.

